6.7.2 Statistical Modeling: Repeated Measure Model: General Estimating Equations (GEE)

The primary analysis method to be applied for all repeated measures efficacy parameters will be a general estimating equation (GEE) model (Hanley 2003, SAS Software 2010). A generalized estimating equation (GEE) procedure will be performed for the repeated measures associated with the clinical efficacy endpoints analysis and associated planned comparisons.

The GEE regression model is of the general form:

$$Y_{ij} = \alpha + \beta_1 X_{1i} + \dots + \beta_n X_{yi} + \beta_{n1} T_{1ij} + \dots + \beta_{nx} T_{xij} X_{xi} + \varepsilon_{ij}$$

Where, we assume that the Y_{ij} follow a Normal distribution with $\text{var}(Y_{ij}) = \sigma^2$, and $\text{cov}(Y_{ij}, Y_{ik}) = \delta$ (exchangeable correlation). It follows that the link function is the identity. The model above has been parameterized with reference cell coding, where the coefficient estimates corresponding to the treatment variables (X_2, X_3) capture the mean differences in the change from baseline for the planned comparison. The model will provide that a test of change from baseline at the planned time points (identified in the comparisons in [Table 8](#)) is the linear estimate of $\beta_3 + \beta_{12}$. The following general form and sample SAS Software program code provides an example of this type of GEE model implementation across the planned efficacy parameters described in [Table 6](#) and [Table 7](#):

```
PROC GENMOD DATA=<data set name>;
  CLASS <id variable>;
  MODEL <efficacy parameter> = <trt1> <trt2> <baseline>
    <covariates> <vx_trt1> <vx_trt2> <interactions> / DIST=NORMAL;
  REPEATED SUBJECT=<id> / CORR=CS;
  ESTIMATE '<planned comparison>' <trt1> 1 <trt2> 1 <vx_trt1> 1;
```

RUN;
QUIT;

where:

<id variable> uniquely identifies the subject: A record for every visit for each subject,
<efficacy parameter> identifies the clinical efficacy parameter of interest,
<baseline> identifies the baseline for the efficacy parameter measure for the subject,
<planned comparison> comparisons identified in [Table 8](#),
<trt1> is the 12g/day SA-ER/SA-IR variable (1,0),
<trt2> is the defined dose for comparisons (1,0),
<vx> are coded (0,1) visit variables,
<vx_trt1>, <vx_trt2> are coded (0,1) visit x treatment interaction variables,
<covariates> define any additional baseline covariates assessed for inclusion in the GEE model at $p < 0.05$.

In general, baseline value, gender, and age will be covariates in the GEE models for each planned analysis where appropriate. The final form of the GEE model for each clinical efficacy parameter and planned comparison will be described in the final study report.

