6.7 Statistical Analysis: Clinical Efficacy

6.7.1 Planned Comparisons for Clinical Efficacy Parameters

The planned comparisons for UX001-CL202 are based on change from baseline assessments, where different baselines are utilized to evaluate treatment across a subject's treatment in

both UX001-CL201 and UX001-CL202. [Table 8](#) presents the planned comparisons for study data obtained in UX001-CL202 compared with study data from UX001-CL201 for roll-over subjects, as well as the treatment naïve subjects in UX001-CL202.

Clinical efficacy data collected in Part I of UX001-CL202 (all roll-over subjects dosed with 6g/day SA-ER) will not be included in planned comparisons for the clinical efficacy analysis.

Additional comparisons not specified in this statistical analysis plan may be completed as prospective analyses are completed to better understand study results. These additional comparisons will be clearly identified in final reporting.

Table 8 Planned Comparisons

Planned Comparison	Description
Primary Analysis #1: Week 24 12g/day SA/ER/SA-IR vs. Week 0	All subjects who roll-over from UX001CL201 will have their week 0 assigned as baseline (Part I termination visit of the 202 study) and the change from this score will be compared to the week 24 12g/day SA-ER/SA-IR treatment to assess the impact of the 12g/day SA-ER/SA-IR dose.
Primary Analysis #2: Week 24 12g/day SA/ER/SA-IR vs. Week 48 UX001-CL201 for 6/6+0/6 SA-ER	All subjects who roll-over from UX001CL201 will have their week 48 assigned as baseline and the change from this score will be compared to the week 24 12g/day SA-ER/SA-IR treatment to assess the impact of the 12g/day SA-ER/SA-IR dose across the combined 6/6+0/6 dose (UX001-CL201 subjects treated with 0/6 or 6/6 SA-ER will be combined for comparison from dosing pathways 1 and 3 from Table 3). A second comparison will be with a 6 minute walk test at Screening of ≥ 200 m (6MWT ≥ 200 m)
Primary Analysis #3: Week 24 12g/day SA/ER/SA-IR vs. Week 48 UX001-CL201 for 3/3+0/3	All subjects who roll-over from UX001CL201 will have their week 48 assigned as baseline and

Planned Comparison	Description

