SA-ER	
the change from this score will be compared to the week 24 12g/day SA-ER/SA-IR treatment to assess the impact of the 12g/day SA-ER/SA-IR dose across the combined 3/3+0/3 dose (UX001-CL201 subjects treated with 0/3 or 3/3 SA-ER will be combined for comparison from dosing pathways 2 and 4 from Table 3)
 
A second comparison will be with a 6 minute walk test at Screening of ≥ 200 m (6MWT≥ 200m)

Secondary Analysis: Stability in endpoint over time and dose from Week 0 UX001-CL201 through Week 24 UX001-CL202. (Trend over time)
	
All subjects who roll-over from UX001CL201 will have their week 0 assigned as baseline and the stability from this baseline score will be assessed over time through the week 24 12g/day SA-ER/SA-IR treatment to assess the impact of dose combinations over time. For this analysis the UX001-CL201 subjects treated with 0/6 or 6/6 SA-ER will be combined for analysis from dosing pathways 1 and 3 and subjects treated with 0/3 or 3/3 SA-ER will be combined for analysis from dosing pathways 2 and 4 (Table 3). Each dosing pathway combination will be a separate analysis to assess the trend in endpoint scores over time and dose.
 
A second comparison will be with a 6 minute walk test at Screening of ≥ 200 m (6MWT≥ 200m)

Treatment Naïve Primary Analysis: Week 24 12g/day SA/ER/SA-IR vs. Week 0 Baseline (Week 12 on T&E)
	
Treatment Naïve subjects who enroll in UX001-CL202 will have a primary comparison of their change from baseline assessment for efficacy parameters.

Treatment Naïve Secondary Analysis: Week 24 12g/day SA/ER/SA-IR vs.
	
Treatment Naïve subjects in UX001-CL202

Planned Comparison	Description
Week 0-24 UX001-CL201 Placebo	endpoint data from week 0 to 24 will be compared to the UX001-CL201 Placebo (for those patients with 6MWT >=200m) treated subjects' endpoint data from week 0 to 24 for change from baseline assessments.

Additional comparisons may be defined upon review of the data to examine trends throughout a subject's treatment course through both UX001-CL201 and UX001-CL202, via the dosing pathways identified in [Table 3](#) and [Figure 1](#).

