6.7.5 Efficacy Analysis: Muscle Strength - Hand Held Dynamometry (HHD)

The hand held dynamometry (HHD) assessment is completed in UX001-CL202 at the Part II time points of Screening/Baseline (last visit in Part I), months 3, 6, 12, 18, 24, 30, 36, and the termination visit (Table 2). The HHD parameters will be summarized into composite scores and GEE analyses will be performed.

HHD Upper Extremity (UE) Composite Score

HHD UE composite scores will be used to evaluate change in upper extremity muscle strength. HHD UE composite scores achieved for the 12g/day SA-ER/SA-IR dosing group at each study time point will be evaluated using descriptive statistics.

A GEE model (see Section 6.7.2) will be completed for the week 24 (6 month) analysis and will include the visits from Part II of UX001-CL202 (Months 1 to 6) accounting for time on the 12g/day SA-ER/SA-IR treatment with subjects who cross-over from treatment administered in UX001-CL201 (Table 3). The primary model will incorporate the treatment groups defined in the planned comparisons (Table 8).

HHD Lower Extremity (LE) Composite Score

HHD LE composite scores will be used to evaluate change in lower extremity muscle strength. HHD LE composite scores achieved for the 12g/day SA-ER/SA-IR dosing group at each study time point will be evaluated using descriptive statistics. The same modelling strategy applied for the HHD UE will be applied for the HHD LE Composite score.

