6.7.7 Efficacy Analysis: Six-Minute Walk Test Distance

The Six Minute Walk Test (6MWT) will be used to evaluate change in walking capacity. 6MWT distance observed for the 12 g/day SA-ER/SA-IR treatment group will be summarized using descriptive statistics at each time point from Part II of UX001-CL202 (Table 2).

A GEE analysis model will be developed to examine the change in 6MWT distance for the 6-month part II analysis with study time points as categorical predictors and age, gender and Screening 6MWT distance as covariates. The defined baselines and planned comparisons to be examined in this analysis are identified in Table 8.

In addition the cross-over treatment pathway groups may be compared with the change observed in prior treatment period for the 6MWT. Trends in the change observed in 6MWT will be displayed using graphical techniques.

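### SAP 6.7.2 defines its GEE test with two coefficients but its sample ESTIMATE line sums three, and it names no small-sample inference for the roughly 10 treatment-naïve subjects

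*SAP*

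**What the plan says.** SAP 6.7.2 makes GEE the primary method for the repeated-measures efficacy parameters. Its equation has treatment terms, a time term standing alone, and time-by-treatment products. On coding it says "The model above has been parameterized with reference cell coding", without naming the reference cell. It continues: "The model will provide that a test of change from baseline at the planned time points" listed in Table 8 is given by β3 + β12.

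The sample program below that text is offered as an example for the parameters of Tables 6 and 7, and its label points to the Table 8 comparisons. Its contrast is "ESTIMATE '<planned comparison>' <trt1> 1 <trt2> 1 <vx_trt1> 1". The key makes `trt1` the 12 g/day indicator and `trt2` the indicator of the comparison dose. It also states "<vx> are coded (0,1) visit variables", but the MODEL line contains only visit-by-treatment products and never `<vx>` alone. The REPEATED line sets an exchangeable correlation; the section does not mention a variance estimator or degrees of freedom. Further baseline covariates may enter at p < 0.05, and the final form of each model is left to the study report.

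The Table 8 rows are of different kinds. Primary #1 and Naïve Primary are changes from baseline; the naïve subjects "will have a primary comparison of their change from baseline assessment for efficacy parameters". Naïve Secondary is a comparison with CL201 placebo subjects. Primary #2 is meant "to assess the impact of the 12g/day SA-ER/SA-IR dose across the combined 6/6+0/6 dose", which can be read as within-group or between-dose, and #3 has the same form.

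On time, 6.7.7 asks for a model "with study time points as categorical predictors and age, gender and Screening 6MWT distance as covariates", and 6.7.9, 6.7.11 and 6.7.12 are similar. For HHD, 6.7.5 says only "accounting for time on the 12g/day SA-ER/SA-IR treatment". SAP 6.1 plans 10 naïve subjects and allows more. SAP 6.5 sets two-sided significance at 0.05. SAP 6.7.3 permits ANCOVA as a supportive analysis.

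**The concern.** Two coefficients and three coefficients are different tests, so the text and the code cannot both be the planned analysis. One template also cannot serve rows that mix within-group changes with a between-group difference. With no reference cell or per-row contrast fixed, the p-value and interval printed for a Table 8 row depend on choices the SAP has not made and defers until after the data are seen.

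The second issue concerns inference in a very small group. The naïve subjects have their own primary and secondary comparisons at 0.05. A robust GEE variance with a normal reference is too small with about 10 subjects, and neither the SAP nor the protocol names a remedy.

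**Working it through.** **1. Two exclusive groups.** Take 12 g/day and one comparator at two visits, with columns (1, trt1, trt2, vx_trt1, vx_trt2). The four design rows are (1,1,0,0,0), (1,1,0,1,0), (1,0,1,0,0) and (1,0,1,0,1), of rank 4. In every row trt1 + trt2 = 1, the intercept. A contrast with no weight on the intercept is therefore estimable only if its weights on trt1 and trt2 sum to zero.

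| Contrast | Weights on trt1 + trt2 | Rank with contrast added | Estimable |
|---|---|---|---|
| trt1 + trt2 + vx_trt1 (coded) | 2 | 5 | no |
| trt1 + vx_trt1 | 1 | 5 | no |
| trt2 + vx_trt2 | 1 | 5 | no |
| trt2 + vx_trt1 | 1 | 5 | no |
| trt1 − trt2 + vx_trt1 − vx_trt2 | 0 | 4 | yes |

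Matching the code to β3 + β12 would therefore not be enough here. This is the Naïve Secondary situation with placebo as trt2.

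**2. A third reference cell.** All the contrasts are now estimable. At the later visit the between-dose difference is trt1 − trt2 + vx_trt1 − vx_trt2, so the coded line exceeds it by 2·trt2 + vx_trt2. Illustration with invented means at two visits: reference −0.5, −1.5; comparator 0.2, 0.4; 12 g 0.6, 1.0. With the time term included, trt2 = 0.7 and vx_trt2 = 1.2.
- trt1 + vx_trt1 = 2.5, which is 12 g minus reference.
- The coded line gives 3.2.
- The between-dose difference is 0.6, and 3.2 − 0.6 = 2(0.7) + 1.2 = 2.6.

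**3. Single group.** With the subject's own baseline records as reference cell, trt1 + vx_trt1 is estimable (rank 3 stays 3). With follow-up change scores only, it is not (rank 2 becomes 3).

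**4. Time term.** If the two groups are exclusive and cover all records, vx = vx_trt1 + vx_trt2, so omitting `<vx>` leaves the fit unchanged. It changes results only if records with trt1 = trt2 = 0 exist at more than one visit, because that cell is then forced to a single mean.

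**5. Naïve Primary test size.** Assumption: uncorrected sandwich variance with a normal reference. For a mean change this variance is ((n − 1)/n)·s²/n, so the null rejection rate is 2·P(t(n−1) > 1.96·√((n − 1)/n)).

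| n | Cut-off on the t scale | Null rejection | Half-width relative to t interval |
|---|---|---|---|
| 10 | 1.859 | 9.6% | 0.822 |
| 15 | 1.894 | 7.9% | 0.883 |
| 20 | 1.910 | 7.1% | 0.913 |
| 46 | 1.939 | 5.9% | 0.962 |

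Adding baseline value, age and sex does not change this row when the subject's own baseline records are the reference. Those covariates are constant within subject and cancel with complete data; refitting gave the unadjusted mean change to rounding error. The Kauermann-Carroll variance of a simple mean equals s²/n, for which t with n − 1 df is exact. In the refitted model it rejects about 5%; using n − 4 df gives 3–4%.

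**6. Naïve Secondary test size.** The number of placebo walkers is not in the documents. With equal allocation over three arms (assumed) and the 60% walker target of Protocol 7.3, 46 × 1/3 × 0.60 ≈ 9; the range used is 6–15. Simulation: normal data, no dropout, two visits, covariates baseline, age and sex, correlation 0.5–0.9, 20,000 runs per cell.

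| Naïve v placebo | Uncorrected, normal reference | Kauermann-Carroll with t (df = N − 5) |
|---|---|---|
| 10 v 6 | 13.7–15.0% | 5.7–6.0% (df 11) |
| 10 v 9 | 11.5–13.0% | 5.5–5.9% (df 14) |
| 10 v 15 | 9.6–10.5% | 5.2–5.8% (df 20) |

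The uncorrected half-widths are 0.73–0.85 of the corrected ones.

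**The case against.** The code is labelled a sample, is full of placeholders including an undefined interactions slot, and programming details are sent to a separate specification. The study is open-label, not powered and without multiplicity adjustment, and the protocol calls naïve-versus-placebo only a potential comparison. This limits the harm to misleading p-values and intervals. It does not remove the mismatch, because no other contrast is prespecified and SAP 6.3 makes the 6-month analysis primary for efficacy.

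ANCOVA on a single Week 24 value would bring a t or F reference that suits small samples. That is true, but 6.7.3 makes it optional and supportive and does not tie it to the naïve group.

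The variance estimator is not stated, so every rejection rate above rests on an assumption. That objection stands, and it is why the estimator needs to be named.

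Three stronger readings are tempting, and the documents do not support them:
- A reader might infer that the missing time term biases the 12 g effect by a share of the placebo decline. That needs placebo in the reference cell, whereas the key makes the comparison group `trt2`, and then the omission has no effect.
- A reader might infer that covariate adjustment raises the Naïve Primary rejection rate well above 9.6%. That belongs to a change-score model adjusted for baseline, age and sex, not to a contrast against the subject's own baseline records.
- A reader might extend the small-sample problem to the rollover subjects. At n = 46 the unadjusted rate is 5.9%.

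**Conclusion.** The point holds and should be fixed. SAP 6.7.2 contradicts itself on its test, and its coded contrast is either not estimable or not a between-dose difference, depending on a reference cell it does not name. The dropped time term is a consistency correction, and no magnitude is attached to it.

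For the naïve analyses, a stated 5% test would run at 9.6% at n = 10 within group (7.9% at 15, 7.1% at 20) and at about 10–15% for 10 naïve subjects against 6–15 placebo walkers. These rates assume the uncorrected sandwich with a normal reference, normal data and no dropout; the second also assumes the placebo numbers and the three covariates. The estimability result needs none of these assumptions, only that the two groups are exclusive and each has its own indicator.

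**What to change.** 1. In 6.7.2, name the reference cell and write the contrast for each Table 8 row.
   - Primary #1 and Naïve Primary: trt1 + vx_trt1, with the subject's own baseline records as reference.
   - Naïve Secondary: trt1 − trt2 + vx_trt1 − vx_trt2, with placebo as trt2.
   - Primary #2 and #3: state whether the contrast is within-group or between-dose, then write it out.
   - Secondary: write out the trend contrast.
2. Put `<vx>` in the MODEL line wherever the reference cell has more than one visit.
3. Keep the exchangeable GEE of Protocol 7.6.1.1. For the naïve analyses, use the Kauermann-Carroll corrected sandwich with a t reference. Use df = n − 1 for Naïve Primary; n − 4 would be conservative there and applies only if change scores are modelled with baseline, age and sex. Use df = N − 5 for Naïve Secondary (intercept, group, baseline, age, sex).
4. Keep only the prespecified covariates and delete the p < 0.05 entry rule.

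The cost is one table and a few sentences, and possibly a macro or other software, which SAP 6.5.10 allows. With 10 naïve subjects, intervals widen to about 1.2 times for Naïve Primary (1/0.822) and roughly 1.2–1.4 times for Naïve Secondary (1/0.85 to 1/0.73). The corrected Naïve Secondary test is close to nominal (5.2–6.0%) but not exact.

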6.5 General Considerations for Statistical Analysis

All statistical tests will be two-sided and a difference resulting in a p-value of less than or equal to 0.05 will be considered statistically significant. All p-values will be rounded to and displayed in four decimals. If a p-value less than 0.0001 occurs it will be shown in tables as <0.0001.

There will be no multiplicity adjustments, or adjustments for multiple comparisons.

Descriptive summaries of variables will be provided where appropriate. For continuous variables, the number of non-missing values (n) and the median, mean, standard deviation, minimum, and maximum will be tabulated by treatment. For categorical variables, the counts and proportions of each value will be tabulated by treatment. Expansion of descriptive table categories within each treatment may occur if such elaborations are thought to be useful.

All collected data will be presented in listings. Data not subject to analysis according to this plan will not appear in any tables or graphs but will be included in the data listings.

Post-hoc exploratory analyses not identified in this SAP may be performed to further examine the study data. These analyses will be clearly identified as such in the final clinical study report. The SAP will not be amended for post-hoc, additional analyses identified after planned analyses are completed. Likewise, the list of planned tables (Section 8.1) is the list of planned tables prospectively defined for the study analyses. Additional tables and figures may be defined to further evaluate study results and the SAP will not be amended to list these additional analysis tables.

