6.7.9 Efficacy Analysis: Walking Speed Test

Gait Speed – Comfortable and Maximum Pace:

The gait speed test will be used to evaluate walking speed at a comfortable and maximum pace on a 7.62 meter (25 feet) course. The speed at which the subject can walk 7.62 meters will be measured in centimeters/second (cm/s) for the comfortable and maximum paces. Comfortable gait speed (CGS) and maximum gait speed (MGS) observed for the 12g/day SA-ER/SA-IR treatment group in Part II of UX001-CL202 will be evaluated using descriptive statistics.

A GEE analysis model will be developed to examine the change in speed (cm/s) at the comfortable pace (CGS) for the 6-month Part II analysis with study time points as categorical predictors and age, height and Baseline CGS as covariates. The same GEE model will be used to assess change in speed (cm/s) at maximum pace (MGS). The defined baselines and planned comparisons to be examined in this analysis are identified in [Table 8](#).

In addition the cross-over treatment pathway groups may be compared with the change observed in prior treatment period for the CGS and MGS parameters. Trends in the change observed in the CGS and MGS parameters will be displayed using graphical techniques.

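### SAP 6.7.2 admits extra baseline covariates to the efficacy GEE models on p < 0.05 in the trial data, which understates uncertainty in small-group and between-group comparisons

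*SAP*

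**What the plan says.** SAP 6.7.2 makes GEE the primary method for the repeated-measures efficacy parameters and offers SAS code as an "example of this type of GEE model implementation across the planned efficacy parameters described in" Tables 6 and 7. In that code the covariates entry is said to "define any additional baseline covariates assessed for inclusion in the GEE model", with p < 0.05 as the threshold. The section lists no candidates and describes no selection procedure.

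The section closes with two further statements. The first is a soft default: "In general, baseline value, gender, and age will be covariates in the GEE models for each planned analysis where appropriate". The second concerns the model itself: "The final form of the GEE model for each clinical efficacy parameter and planned comparison will be described in the final study report".

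Several endpoint sections name covariates:
- 6.7.7 fits the six-minute walk "with study time points as categorical predictors and age, gender and Screening 6MWT distance as covariates".
- 6.7.9 uses "age, height and Baseline CGS as covariates" for comfortable gait speed, and the same model for maximum speed.
- 6.7.11 (arm lift), 6.7.12 (HIBM-FAS), 6.7.13 (CK) and 6.9.1 (free serum SA) also have lists.

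Sections 6.7.5 and 6.7.6, on HHD, have none and refer back to 6.7.2.

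On testing, SAP 6.5 says: "All statistical tests will be two-sided and a difference resulting in a p-value of less than or equal to 0.05" is significant. It adds: "There will be no multiplicity adjustments, or adjustments for multiple comparisons".

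**The concern.** A covariate retained because it fitted the outcome in this sample removes residual variance that is partly chance. The standard error is then computed as if the covariate had been chosen in advance, so it is too small. In a between-group comparison the treatment estimate moves as well. The reported p-value reflects neither effect.

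The endpoints most exposed are the strength measures. The planned list in SAP 8.1 runs from Table 15 to Table 506 for the individual parameters: 506 − 15 + 1 = 492 tables, at 12 per parameter (one summary, 11 analyses), so 41 parameters. HHD supplies 28 of these: 13 raw muscle groups, 13 percent-predicted versions and 2 composites. None of the 28 has a covariate list that would displace the rule.

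The protocol's account of the repeated-measures analysis (7.6.1.1) has an exchangeable structure and categorical time-by-treatment effects, with no covariate selection step. SAP 6.5.1 nevertheless describes the SAP as consistent with the protocol.

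**Working it through.** The documents give no error rate for this procedure beyond the nominal two-sided 0.05, so there is no stated figure to reproduce. The check asks what happens to that 5% when there is no effect and every extra candidate is noise.

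**Inputs from the documents.** Entry threshold p < 0.05; core covariates baseline value, age and gender; exchangeable working correlation (SAP 6.7.2). About 46 rollover and 10 naive subjects (SAP 6.1). HHD at Months 3 and 6 within the six-month window (SAP Table 2).

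**Assumptions.** Number of candidates K = 3, 5 or 10; comparator of 10 or 15; pathway-type subgroups of 23 or 24; within-subject correlation 0.6.

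**Step 1: chance that noise enters.** With independent candidates, P(at least one enters) = 1 − 0.95^K, which is 14.3% for K = 3, 22.6% for K = 5 and 40.1% for K = 10.

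**Step 2: selection alone.** Least squares on the Week 24 change with exact t-tests, 6,000 datasets per row. Each candidate is tested on top of the core model, those with p < 0.05 are kept, and the model is refitted. Monte Carlo error is about 0.3 points. The SE ratio is mean reported SE divided by the true SD of the estimate.

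| Setting | K | Type I error, fixed | Type I error, selected | SE ratio, fixed | SE ratio, selected |
|---|---|---|---|---|---|
| 46, single group | 3 | 4.8% | 5.0% | 1.01 | 1.01 |
| 46, single group | 10 | 4.9% | 5.6% | 1.00 | 0.97 |
| 24, single group | 10 | 4.9% | 6.6% | 0.98 | 0.92 |
| 10, single group | 3 | 5.1% | 6.8% | 0.96 | 0.91 |
| 23 v 23 | 10 | 4.9% | 6.4% | 1.00 | 0.94 |
| 10 v 15 | 3 | 5.0% | 5.7% | 0.99 | 0.96 |
| 10 v 15 | 10 | 4.7% | 7.4% | 1.00 | 0.89 |

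Further runs of 8,000 datasets gave 5.2% to 6.5% (10 v 15, K = 5), 5.1% to 7.9% (10 v 15, K = 10), 5.1% to 6.7% (10 v 10, K = 5) and 5.3% to 8.4% (10 v 10, K = 10). A separate repeat of 10 v 15 gave 5.0% to 5.7%, 4.6% to 6.1% and 4.8% to 8.1% for K = 3, 5 and 10.

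**Step 3: the estimator the SAP names.** Exchangeable GEE, two visits, uncorrected sandwich SE, Wald test, 3,000 datasets; Monte Carlo error 0.4 to 0.7 points.

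| Setting | K | Fixed | Selected | Difference (points) |
|---|---|---|---|---|
| 46, single group | 10 | 5.7% | 6.7% | 0.9 |
| 24, single group | 10 | 8.4% | 11.1% | 2.7 |
| 10, single group | 3 | 15.3% | 20.7% | 5.4 |
| 23 v 23 | 10 | 7.3% | 9.4% | 2.1 |
| 10 v 10 | 5 | 10.4% | 15.0% | 4.6 |
| 10 v 15 | 5 | 10.2% | 13.2% | 3.0 |
| 10 v 15 | 10 | 10.1% | 15.2% | 5.1 |

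(Differences are taken before rounding.) The entry test shares the small-sample fault, so noise enters more often than in Step 1: 52.7% of datasets for 10 v 15 with K = 5, against 22.6%.

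**Step 4: within-subject contrasts.** Suppose both treatment periods of each subject are in the model, data are complete, and the covariate has no time interaction. A covariate constant within subject cancels from each subject's between-period difference. Under exchangeable correlation with balanced data it is also orthogonal to the period contrast. Estimate and SE are therefore unchanged. A numerical check with 46 and 24 subjects and 5 noise candidates agreed to 1e-15, although a noise covariate entered in about 40% to 46% of runs.

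**The case against.** The best reply is that the rule is softer and narrower than it looks. It defines a placeholder in sample code. Baseline has its own slot there, so the covariates slot may be simply where age and gender go. Most non-HHD endpoints have their own lists with no p-value step. Rollover subjects contribute earlier periods as well as the 12 g/day period, so Primary Analyses #2 and #3 in Table 8 may be within-subject contrasts, which the rule cannot affect when data are complete. The naive-versus-placebo comparison, where the inflation is clear, is only the Treatment Naïve Secondary Analysis. Ten independent candidates is high: beyond age and sex, SAP Table 4 offers race, ethnicity, height, weight, BMI, BMI category and interval history, several of them overlapping. Finally, SAP 6.1 says the study is not powered for significance testing.

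Much of this stands, and it limits the size. The lower candidate counts are the more realistic ones, and the full rollover group is barely touched. It does not remove the point. The p < 0.05 threshold is written down, the endpoint lists do not switch it off, and HHD has nothing else to rely on. Where change scores from a single period are modelled, which Table 8 does not rule out, selection does act. The SAP also labels analyses primary and declares significance at 0.05, whatever it says about power.

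**Conclusion.** The concern holds in a limited form. SAP 6.7.2 contains a data-driven entry rule with no candidate list, and following it makes reported standard errors too small where selection can act: between-group comparisons and small groups, chiefly the roughly 10 naive subjects and the pathway subgroups. With 3 to 10 assumed noise candidates and 10 v 10 to 15 subjects, exact-t type I error goes from about 5% to about 6–8%. For the full rollover group of 46 the excess is under 1 point; for within-subject contrasts with complete data it is nil. Candidate counts, comparator sizes and correlation are assumptions.

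A reader might infer three stronger things that the documents and the check do not support:
- That every efficacy model is affected. Step 4 shows otherwise.
- That models will be chosen after results are known. SAP 6.7.2 says only that the final form will be described in the report, and SAP 1 says the SAP is finalised before any inferential or descriptive analysis.
- That fixing the covariates restores 5%. Under the uncorrected sandwich SE, the fixed model still ran at 5.7% to 15.3%. That is a separate problem, and often the larger one.

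**What to change.** In SAP 6.7.2, delete the clause admitting covariates on p < 0.05 and state that covariates are fixed before analysis, as follows:
- Endpoints with a list keep it as written: 6.7.7, 6.7.9, 6.7.11, 6.7.12, 6.7.13 and 6.9.1.
- HHD endpoints, and any other endpoint without a list, use baseline value, age and gender.
- The same set applies to every comparison of an endpoint.
- A model with further covariates is reported only as a labelled sensitivity or post hoc analysis. SAP 6.5 already requires post hoc work to be identified.

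A single set imposed on all endpoints would be wrong, because it would override the lists for the six-minute walk, CK and free SA.

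The cost is a few sentences of SAP text. The one downside is that a strong prognostic factor nobody planned for can be used only in the labelled model.
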